**2. Study setting and sample.**

**a. Setting.** The study will be implemented in partnership with the outpatient oncology unit at the Grady Cancer Center for Excellence (GCCE). The GCCE is located within the Grady Healthcare System which is a public hospital with nearly 600,000 patient visits each year. The majority of revenues generated through Medicare and Medicaid reimbursement. The Georgia Cancer Center for Excellence (GCCE) at Grady was established by the Georgia Cancer Coalition as part of an initiative to build a statewide network of people and organizations to provide exceptional cancer treatment for all Georgians. *In 2015, GCCE provided care to 1308 cancer patients (674 men/630 women).*

**b. Population to be studied:** For this feasibility study, we will recruit a total of 40 dyads with

a recent cancer diagnosis. Patient inclusion criteria captures patients (age 30-89 years) with 1) newly diagnosed with any stage cancer; 2) treatment plans to include weekly outpatient chemotherapy; 3) previously screened and with greater than 0 level of psychological distress; and, 4) willingness to participate in all study activities including data collection; 6) willing to identify a FCG (immediate or extended family member) to participate. Participants will be excluded if they have completed surgery with no plans for chemotherapy; if they find conversations around religion or spirituality emotionally upsetting; if completed more than half of prescribed chemotherapy treatments; or, in hospice care. We will also exclude participants not able to provide informed consent.

**FCG (immediate or extended family member) Inclusion Criteria are:** 1) 18 years or older; 2) able to provide informed consent; and, 3) willingness to participate in study activities including data collection. FCG's will be excluded if they find conversations around religion or spirituality emotionally upsetting.

- c. **Sample size justification:** Since this is a feasibility study, our aim will be to compute effect sizes that will guide power calculation for testing intervention effectiveness in a future RCT. Preliminary power calculation indicated that group sizes of 40 dyads (total sample 80) will achieve 80% power to detect a minimum difference of 0.6 in a repeated measurements design having a Compound symmetry covariance structure (standard deviation of 1, within subject correlation of 0.2, and an alpha level of 0.05 assumed).

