to identify the factors and strategies that affect health outcomes over time and serve to provide preliminary data to support a larger test of the intervention. These points will also allow for comparisons with other long-term investigations of psychological distress among cancer patients. At baseline data collection we will collect demographic characteristics of participants including age, gender, education, marital status, occupation, employment status, religious affiliation, proximity to family, type and stage of cancer, type treatment, date of diagnosis, date of treatment, and psychological distress screening scores. All data collection will be conducted by phone or video conferencing platform. There will be an 6th optional open-ended interview after the interview sessions to further explore sources of and expressions of distress among participants.

*Demographic and clinical characteristics.* For patients, we will collect data on psychological distress levels (the NCCN Distress score from patient records and the Hospital Anxiety, Depression Scale (HADS)), type and staging of cancer, and type of cancer treatment by either chart review or self-report. For patients and FCGs we will collect information on age, gender, education level, health status, religious affiliation, religiosity, insured status, income, and geographic residence. The religiosity scale measures frequency of using spiritual practices such as the use of religious songs, reading religious materials, and, attending church. Collection of data for demographic and clinical characteristics will occur immediately after obtaining informed consent and before viewing the video narratives.

*NCCN Distress Scale (National Comprehensive Cancer Network)* is a well-known screening tool for distress. In the GCC, this tool is administered to all newly diagnosed cancer patients. This screening tool is a thermometer on which patients rate their distress on a level of 0-10 with 10=extreme distress and 0=no distress. The NCCN-DT will be obtained from patient records to determine eligibility for this study. We will only recruit patients with a NCCN-DT score of  $\geq 4$  which is likely indicative of high levels of distress.

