*Psychological distress* levels for cancer patients will be measured with the Hospital Anxiety, Depression Scale (HADS). The HADS is a 14-item self-report scale for anxiety and depressive states for patients. Internal consistency with African American oncology patients has ranged from .77 (Anxiety) and .78 (Depression). The HADS is sensitive to change after integrative therapy interventions with scores for Anxiety (8.20 $\pm$ 4.34 to 5.79 $\pm$ 3.64); Depression (5.97 $\pm$ 4.00 to 3.96 $\pm$ 3.23). Scoring for the Anxiety and Depression Subscales of the HADS is (0-21); Normal (0-7); Borderline Abnormal Case (8-10); and Abnormal Case (11-21). Patients and family caregivers will be asked to complete this evaluation at baseline and after all of the intervention sessions.

*Quantitative Assessment of narrative quality (narrative characteristics, identification, transportation)*. Assessment of narrative quality (narrative characteristics, identification, and transportation) will be examined using the Narrative Quality Assessment Tool. Narrative characteristics will be examined using a 9 item scale that measures perceived likability of characters in the story, emotional relevance of the storyline, and cultural elements of the stories. Identification will be examined using a 8-item scale that measures the degree to which participants are able to relate to the characters in the video recordings or perceive their story to be similar to their own. Transportation (engagement) will be examined using a 6-item scale

that measures participants emotional connections to the stories in the video recordings. Response options will be on a 5-pt scale and similar to that in other questionnaires in this pilot (1=not at all to 5=quite a bit). Internal consistency for the three scales range from .92 - .95 respectively. Validity was determined through hypothesized factor structures (CFA). Patients and family caregivers will be asked to complete these evaluations after each intervention session.

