#### **10. Plans for analysis, statistical and/or otherwise:**

- a.** Data analysis will occur on a password protected computer and data stored on servers provided by Emory University.
- b.** Specifically, we will use structured and unstructured interviews to explore influences of identification, engagement, and emotional response to the intervention. We will also explore qualitatively participant experiences with the use of hymns as a coping strategy.

Statistical software: SAS v9.3 will be used for all quantitative statistical analyses.

Quantitative descriptive analyses will be used to describe the baseline characteristics, interrater reliability, and frequencies and rankings of evaluations of video recorded narratives among study participants. The chi-square and Fisher's exact tests (cells smaller than five) will be used to determine differences in the participant responses to the video-recorded narratives according to gender (male vs. female) and patient vs. family caregiver.

Atlas.ti will be used to manage and analyze qualitative data. A qualitative descriptive design  using open-ended semi-structured interviews and qualitative content analysis  will be used to elicit and analyze patient and FCG response to transportation.

**Aim 1: Develop a series of professionally edited narrative video recordings** of African American cancer patient and FCG survivorship narratives that are grounded in the strong spiritual culture of African Americans. The recordings will be professionally edited to capture concepts of Stress and Coping Theory and include content of patient/FCGs describing the psychological stressors encountered, and faith-based strategies used to in response to the psychological distress experienced, and health outcomes. The selection of video recorded narratives for the pilot test will consist of those that capture a complete story (stressful cancer experience, faith-based coping strategy used, and health outcome) and deemed to have appropriate sound and visual quality. We will also review the final selection to ensure characters in the video recordings vary by age, gender, and type cancer.

**Aim 2: Pilot test for usability and evaluation of transportation.** A combined quantitative and qualitative methodology will be used to examine transportation of the video

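### Gender and patient/caregiver role are tested without stratifying or adjusting one for the other, so if the gender mix differs by role, a role difference in the ratings can be reported as a gender difference, and the reverse.

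*Combined protocol and SAP*

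**What the plan says.** All references are to the combined protocol and SAP.

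- **Tests.** Section 10 (plans for analysis) names chi-square tests, and Fisher's exact test for small cells, to find "differences in the participant responses to the video-recorded narratives according to gender (male vs. female) and patient vs. family caregiver". It gives no stratified test, no model with both factors and no gender comparison within role. The rest of the quantitative plan is means, frequencies and percentile rankings.
- **Who is rated.** Section 2.b states "we will recruit a total of 40 dyads", which means 40 patients and 40 caregivers. On the narrative-quality scales: "Patients and family caregivers will be asked to complete these evaluations after each intervention session".
- **Gender mix.** Section 2.a reports that in 2015 "GCCE provided care to 1308 cancer patients (674 men/630 women"). No figure is given for caregivers. Eligibility asks only for an adult member of the immediate or extended family.
- **Data available.** Under demographic and clinical characteristics: "For patients and FCGs we will collect information on age, gender, education level". Role is known by design, so a joint analysis needs nothing extra.

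The plan does not say in words that the factors are tested one at a time in the pooled sample. That is an inference, but the natural one: each named test sets one grouping factor against one response, and nothing else is specified.

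**The concern.** Role and gender are linked in the sample whenever patients and caregivers differ in gender mix. If caregivers are mainly women, the men in the pooled sample are mainly patients. A male-female comparison is then partly a patient-caregiver comparison. A pure role difference can show up as a gender difference, and a real gender difference can be exaggerated or masked. The role comparison has the mirror-image problem.

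This is confounding. It is separate from the fact that the two members of a dyad are correlated: a paired or clustered test of one factor corrects the standard error but leaves the contrast mixed.

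At stake is whether the gender and role differences that the study reports carry the right label. These are the only two subgroup comparisons of the ratings that the plan names.

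**Working it through.** The plan gives no design figure for these tests. Its sample-size statement (section 2.c) concerns a different comparison and does not bear on this point.

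**Inputs**
- From the documents: 40 dyads. Men among clinic patients = 674/(674 + 630) = 674/1304 = 51.7%, women 48.3%. The two counts sum to 1304, not 1308, so 1304 is the denominator.
- Assumed: study patients resemble the clinic's; caregivers are 52%, 60%, 75% or 85% female; the role difference is 0.5 or 0.8 SD; the within-dyad correlation is 0.3; there is one rating per person, split at the median (the plan does not say how responses are categorised).

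**Step 1: how much of a role difference enters the gender contrast**

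Crude gender difference = true gender difference + L × role difference, where L = P(patient | man) − P(patient | woman). With equal numbers of patients and caregivers, and m the male share of caregivers:

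L = 0.517/(0.517 + m) − 0.483/(0.483 + 1 − m)

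| Caregivers female | L | Spurious gender difference at 0.5 SD | at 0.8 SD |
|---|---|---|---|
| 52% (all opposite-sex partners) | 0.517 − 0.483 = 0.03 | 0.02 SD | 0.03 SD |
| 60% | 0.564 − 0.446 = 0.118 | 0.06 SD | 0.09 SD |
| 75% | 0.674 − 0.392 = 0.282 | 0.14 SD | 0.23 SD |
| 85% | 0.775 − 0.362 = 0.413 | 0.21 SD | 0.33 SD |

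**Step 2: the reverse direction**

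The share of a gender difference that enters the role contrast is 0.517 − m. That is 0.12, 0.27 and 0.37 at 60%, 75% and 85% female, and 0.03 with all opposite-sex partners.

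**Step 3: how often the gender test rejects at 5% when there is no gender effect**

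Simulation of 3,000 studies of 40 dyads, chi-square on a median split:

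| Caregivers female | 0.5 SD role difference | 0.8 SD role difference |
|---|---|---|
| 60% | 6.3% | 5.9% |
| 75% | 7.5% | 12.4% |
| 85% | 10.9% | 19.4% |

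A repeat run gave 6.2%, 7.9% and 9.6%, and 6.5%, 12.4% and 18.4%. With all caregivers opposite-sex partners, the rates were about 3% and 4%, below nominal.

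**Step 4: cross-check with binary ratings**

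Assume a favourable rating from 50% of patients and 80% of caregivers, whatever their gender, and independent ratings. The gender chi-square rejects in 5–6% of studies with 48% female caregivers, 7% at 60%, 9–11% at 70%, 16–17% at 80% and 26% at 90%. Stratifying by role brings this to 4.8–5.3% throughout. With correlated ratings in mostly opposite-sex pairs, the stratified test rejects in 3.0–4.4%: it is conservative because it ignores the pairing.

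**Step 5: the joint model**

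With role and gender together and dyad correlation allowed for, under the Step 3 assumptions and caregivers 60% to 85% female, the gender test rejects in 5.1–6.4% and the mean bias is at most 0.005 SD.

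**The case against.** **The bias may not arise.** It needs both an unequal gender mix and a sizeable role difference, and the documents give neither. The 51.7% is the clinic's whole 2015 caseload, not the eligible patients. If most caregivers are opposite-sex partners, the mixing almost vanishes. This stands, and it makes the point conditional. It does not rescue the plan: the mix is unknown in advance, and unadjusted tests give no protection if it is skewed.

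**A crude contrast can be what is wanted.** Section 10 asks whether responses differ by gender and makes no claim about gender apart from role. That is fair for a descriptive pilot table. But a reader of a gender test will take it to be about gender, and a table of gender within role would give both views.

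**Consequences.** A reader might infer that recordings could be wrongly chosen or edited. The documents do not support that. Section 10, Aim 2 retains the top half by overall percentile ranking and ties editing to the interview data. The chi-square and Fisher results have no stated role in either.

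**Larger error rates.** A reader might also treat the scales as continuous and arrive at about 14% (0.5 SD) or 26% (0.8 SD) with 85% female caregivers. Those come from a t-test on scale means, which is not planned. On the same assumptions, chi-square gives 11% and 19%.

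**Conclusion.** The point holds in conditional form. The plan names unadjusted tests for two factors that may be associated in its own sample, and nothing in it separates them. With caregivers 60% to 85% female, between 12% and 41% of any role difference passes into the gender contrast, and the false-positive rate for gender runs from about 6% to 11% (0.5 SD) or 19% (0.8 SD). With a balanced caregiver mix it stays near or below 5%. All of this assumes patients like the clinic's, a within-dyad correlation of 0.3 and no true gender effect.

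The effect stops at the reported exploratory comparisons of a feasibility study. It does not reach the selection of recordings. It is worth correcting because the remedy uses data already planned.

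**What to change.** In section 10, for each narrative-quality scale (narrative characteristics, identification, transportation), fit one model with role and gender together and dyad as the cluster. Report the gender difference adjusted for role and the role difference adjusted for gender, each with a 95% CI.

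For single categorical items, tabulate responses by gender within role and test gender with a Cochran-Mantel-Haenszel test stratified by role. Use an exact version where cells are sparse: at 85% female there would be only 0.15 × 40 = 6 male caregivers. State that this test ignores the dyad pairing.

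**Cost:** plan wording and a few more lines of analysis code, with no new data. The gender CI widens slightly if nearly all caregivers are one gender: at 85% female the standard error goes from about 0.24 to 0.25 SD, or 0.25/0.24 = about 4% wider.

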**10. Training of study team:**

The PI or RA will conduct all interviews and will have completed CITI training at Emory.

**11. Plans for monitoring the study for safety:**

This study is no more than minimal risk.

**12. Confidentiality:**

All interviews will be conducted by telephone or video conferencing platform. To maintain confidentiality of the data, each participant will be assigned a subject identification number. The subject identification number will be used to keep track of recorded interviews and transcribed data. Identifying information associated with the subject identification numbers will be kept separate from the data at all times. Digitally – recorded interviews and hard copies of transcribed interviews will be kept on a password protected computer. Data files of transcribed interviews and a database with the research participants' information will be kept on a secure server that can only be accessed by authorized personnel with valid user id and password. Identifiers to the data will be destroyed once data is analyzed, published. However, the PI will retain identifiers to data of participants who have given written consent for the interviews to be used in future testing of this intervention.
